9. ADVERSE EVENTS

Throughout the course of the study, the investigator must remain alert to possible adverse events or untoward findings. If adverse events occur, the first concern will be the safety of the subject. Appropriate medical intervention will be provided by the investigator.

Adverse Event (AE) Definition: An AE is any untoward medical occurrence associated with the use of a study drug in a clinical investigation subject, whether or not considered related to the study drug.

Adverse Event Reporting Period: The AE reporting period for this trial begins upon signing the ICF and ends at the completion of the subjects' final study visit exam. All AEs reported by the subject during the course of the study, or elicited by questions from the investigator, or noted as a result of procedures carried out on the subject, during the AE-reporting period must be recorded by site staff in the source documents and on the AE eCRF, whether or not the event is considered related to the study drug. In addition, any known untoward event that occurs subsequent to the AE reporting period that the investigator assesses as related to the study drug should also be reported as an AE.

Serious Adverse Event (SAE) Definition: A serious adverse event (SAE) or reaction is any untoward medical occurrence that at any dose:

- Results in death
- Is immediately life-threatening or immediately sight-threatening in a treated eye(s)
- Requires inpatient hospitalization or prolongation of existing hospitalization
- Results in persistent or significant incapacity or substantial disruption of the ability to conduct normal life functions
- Is a congenital anomaly/birth defect
- Is an important medical event that may jeopardize the subject or may require medical intervention to prevent one of the outcomes listed above

SAE Reporting: SAEs must be immediately reported (within 24 hours of awareness of the event) to designated contract research organization (CRO) and will be clearly documented in the source documents and on the appropriate AE eCRF and SAE Report Form. The investigator must also notify the IRB of any SAEs, according to the IRB's guidelines.

Pre-existing Conditions: In this trial, a pre-existing condition (i.e., a disorder present before the AE-reporting period started and noted on the Systemic and/or Ocular Medical History Forms) should not be reported as an AE unless the condition worsens or episodes increase in frequency or severity during the AE-reporting period.

BCVA: A worsening of 3 lines or more in log of the minimum angle of resolution (logMAR) score in the study eye from baseline or any prior visit should be captured in the source documents and on the appropriate eCRF as an AE.

IOP: An increase from baseline or any prior study visit of 10 mmHg in IOP in the study eye should be captured in the source documents and on the appropriate eCRF as an AE. An IOP of 30 mmHg or higher will be reported as an SAE.

Biomicroscopy: Slit lamp biomicroscopy will be performed to observe the overall health of the eye, including the lid/lashes, conjunctiva, cornea, anterior chamber, iris, and lens. Any biomicroscopy observations noted prior to Screening (Visit 1) should be recorded as ocular medical history. Any treatment-emergent findings (i.e., findings that were not present prior to treatment or a worsening relative to the pretreatment baseline) should be recorded as an AE.

Ophthalmoscopy: A new finding or a significant worsening (2 units or more) from baseline should be recorded as an AE.

AE Considerations: Additional exams may be scheduled as necessary to ensure the safety of the subjects during the study period. Subjects discontinued due to an AE should be seen for post-study follow-up visits, as needed. Adverse events considered related to study drug that have not resolved or stabilized by the final study visit will be followed during post-study follow-up visits at the discretion of the investigator until the incident has resolved or stabilized and will be documented in the source documents and AE eCRF. Where appropriate, additional written reports and documentation will be provided. Adverse events considered not related to study drug that have not resolved or stabilized by the final study visit will be noted as ongoing in the eCRF, followed at the discretion of the investigator, and recorded in the source documents.

Pregnancy: Although pregnancy is not considered an AE, any complication related to pregnancy would be considered an AE and recorded in the source documents and, if applicable, on the AE eCRF. If an SAE is associated with the pregnancy, the SAE should be reported on the SAE Report Form.

10. STATISTICAL ANALYSES

10.1. Randomization, Stratification, and Masking

Eligible subjects will be randomly assigned to each of the SURF-200 and vehicle groups in a 1:1:1 ratio according to a validated SAS® computer-generated central randomization schedule. The randomization schedule contains the coded treatment assignments for each randomization number. The randomization plan will be based on the study design, number of treatment groups and number of sites.

The randomization is generated by an un-masked statistician who is not affiliated with the study. The randomization plan will be based on the study design, number of treatment groups, and number of sites. It is shared with the Sponsor's designee responsible for final clinical packaging and labeling to allow for proper packaging and labeling of the study drug supply. Access to the randomization code will be strictly controlled according to the Sponsor designee's Standard Operating Procedures (SOPs).

The randomization is not unmasked until the study is complete and the database is locked. The Sponsor will confirm in writing that there are no regulatory or quality issues which preclude the unmasking of the study.

Unmasking of the randomization code prior to study completion due to a medical emergency will be managed in accordance with the Sponsor designee's SOP. All unmasked cases will be fully documented. Otherwise, the study mask will remain intact.

In this double-masked study, the investigator and his/her study staff, the subject (including caregiver, if applicable) and Sponsor/designee (other than as stated above) are masked to the identity of the study drug.

10.2. Efficacy and Safety Variables

Primary Efficacy Endpoint:

- The primary endpoint is the proportion of subjects with clinically significant improvement from baseline in UNC DEMS score at Visit 3 (Day 8). A clinically significant improvement is defined as a minimum reduction in UNC DEMS score of 1 unit or more. Subjects who receive another therapeutic treatment for the signs and symptoms of their episodic flare up due to a lack of efficacy at or prior to Visit 3 (Day 8) will be treated as failures.

Secondary Efficacy Endpoints:

- The proportion of subjects with clinically significant improvement from baseline in UNC DEMS score at Visit 4 (Day 15). A clinically significant improvement is defined as a minimum reduction in UNC DEMS score of 1 unit or more. Subjects who receive another therapeutic treatment for the signs and symptoms of their episodic flare up due to a lack of efficacy at or prior to Visit 4 (Day 15) will be treated as failures.
- The proportion of subjects with clinically significant improvement from baseline in conjunctival hyperemia (using a consistent light source, examiner and exam room from visit to visit) in the study eye at Visit 3 (Day 8). A clinically significant improvement is defined

as an improvement of 0.5 points or more. Subjects who receive another therapeutic treatment for the signs and symptoms of their episodic flare up due to a lack of efficacy at or prior to Visit 3 (Day 8) will be treated as failures.

Safety Variables: AEs (including SAEs), BCVA, IOP, biomicroscopic and ophthalmoscopic findings.

10.3. Analysis Populations

Intent-to-Treat Population: The Intent-to-Treat (ITT) population includes all randomized subjects regardless of whether post-baseline measures are collected, or study drug is received. Subjects in the ITT population will be analyzed in the treatment group to which they were assigned by the randomization schedule, regardless of which study drug they receive.

Per Protocol Population: The per-protocol (PP) population includes all subjects who received at least one dose of study drug and had no significant protocol deviations.

Safety Population: The safety population includes all subjects who receive at least 1 dose of the study drug. Subjects in the safety population will be analyzed in the treatment group for the study drug they received.

10.4. Data Handling: Handling of Missing Data

All missing data will generally not be imputed unless otherwise specified. For subjects who are withdrawn from the study prior to study completion, all data compiled up to the point of discontinuation will be used for analysis. All study discontinuations will be included in all analyses up to the time of study discontinuation.

For the classification of treatment emergent adverse events (TEAEs) and concomitant medications, the following will be applied in case of missing/incomplete dates:

- If all dates/times (start and stop) are missing, the event/medication will automatically be classified as a TEAE/concomitant medication.
- For AE/medication with a missing start date/time, if the event end date/time is prior to first study drug administration, the event will not be classified as a TEAE/concomitant medication, as applicable.
- If only the AE start year/medication end year is present and is the same or is after the first study drug administration year unit, the event/medication will be classified as a TEAE/concomitant medication, as applicable.
- If the AE start month and year/medication end month and year are present and are the same or after the first study drug administration month and year units, the event/medication will be classified as a TEAE/concomitant medication, as applicable.

10.5. Statistical Methods: General Considerations

All final statistical analyses will be performed after the study database has been locked, unmasked, and released for statistical analysis. All tables, statistical analyses, figures, and subject data listings will be generated using SAS® Version 9.4 or later (SAS Institute Inc., Cary, North Carolina, United States of America).

All data in the database will be presented in the data listings. Unless otherwise stated, all listings will be sorted by treatment group, subject number and assessment visit, as appropriate.

Unless otherwise stated, continuous variables will be summarized using descriptive statistics including number of non-missing observations (n), mean, standard deviation (SD), median, minimum and maximum values. The minimum and maximum values will be presented to the same number of decimal places as the eCRF or laboratory reported data; mean, SD, and median will be presented to one more decimal place than the source data.

Categorical variables will be summarized with frequency counts and percentages. The population size (N for sample size and n for available data) and the percentage (of available data) for each class of the variable will be presented. Percentages will be rounded to one decimal place, with the denominator being the number of patients in the relevant population, unless otherwise stated.

Only data from nominal protocol scheduled visits will be included in the summary tables. Data from unscheduled visits will not be included in the summary tables but will be included in the figures and listings.

It should be noted that in this study the analysis unit is subject. When data from both eyes are available, data will not be pooled together for the analysis because eyes from the same subject are not independent samples. Statistical analysis generally requires independent samples. Each subject has a designated study eye as per the protocol. Therefore, separate analysis will be conducted for study eye and fellow eye as appropriate.

All confidence intervals (CIs) of the parameter estimates will be two-sided and at the significance level of 0.05 unless otherwise stated.

All data summaries and data listings will use the nominal visit names as captured in the eCRF and as per the protocol schedule of visits. Derived visit windows will not be used for the data analysis. For all ‘by visit’ summary analyses of efficacy and safety endpoints, if a subject has an early discontinuation before Visit 6/Day 84, the data from the early discontinuation visit will be included in Visit 6/Day 84 assessment. If a subject has an early discontinuation after Visit 6/Day 84 but before Visit 7/Day 98, the data from the early discontinuation visit will be included in Visit 7/Day 98 assessment.

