10.6. General Derived and Transformed Data

Age, in completed years, at informed consent date will be defined as: Age (years) = integer value (Date of Informed Consent – Date of Birth + 1) / 365.25).

Study day will be calculated using the first dosing date as the reference date. If the date of interest occurs on or after the first dosing date, then study day will be calculated as (date of interest – date of first dosing) + 1. If the date of interest occurs prior to the first dosing date, then study day will be calculated as (date of interest – date of first dosing). The day of the first dosing will be identified as Study Day 1 according to Clinical Data Interchange Standards Consortium (CDISC) standard. If a subject is dosed but dosing dates are missing, then the randomization date will be used as the first dosing date for the calculation of study day. Data listings will present study days in addition

to assessment dates, where applicable. As per above, all data summaries and data listings will use the nominal visit names as captured in the CRF and as per the protocol schedule of visits. The calculated study day as per CDISC will only be used in data listings to indicate the distance of an event from the dosing day.

Baseline will be defined as the last available, non-missing observation prior to the first dosing time with study drug, unless specifically mentioned otherwise. When baseline is derived, all data before the first dosing with study drug, including unscheduled visits before the first dosing with study drug, will be used for the derivation of baseline value.

Change from Baseline: Assessment value at post-dosing visit – baseline value. It should be noted that if the derived baseline as above is missing for one parameter, then the change from baseline will not be available for this parameter. Imputation of baseline data will not be conducted.

Percentage Change from Baseline:

$$(\text{Assessment value at post-dosing visit} - \text{baseline value}) * 100 / \text{baseline value}$$

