12. SAFETY

12.1. Adverse Events

Adverse events will be summarized separately for those occurring in the study eye, in the fellow eye, and non-ocular events. For overall AE incidence summary, one table for ocular AEs (study eye and fellow eye combined) will be reported. In this table, each subject will be counted only once in each summary category, to avoid correlated data. However, the results should be interpreted with caution because fellow eyes are selective samples by study design. Regardless of whether the fellow eye is treated or not, all AEs reported for the fellow eye will be included for the safety analysis. AEs marked as 'Both Eyes (OU)' from the AE CRF page will be summarized both for study eye and fellow eye.

All AE verbatim terms will be coded using Medical Dictionary for Regulatory Activities (MedDRA) version 23.0 Update. Terms will be coded to the full MedDRA hierarchy, but the system organ class (SOC) and preferred term (PT) will be of primary interest for the analysis.

Treatment emergent adverse events (TEAEs) are defined as AEs that first occurred or worsened on or after the date of first administration of study drug. If missing dates or time prevent a clear determination as to whether the AE is treatment emergent, the AE will be regarded as a TEAE.

While all AEs will be summarized, the main AE summaries will be restricted to TEAEs only. Treatment emergent adverse events will be summarized descriptively. For the summary of TEAEs, if a subject experienced the same AE multiple times, this will only be counted once for the purpose of counting the number of patients experiencing that AE. Summary tables will include the number of subjects (%) experiencing an AE and the number of AEs.

The TEAE summaries will include:

- Overall Summary of Subjects with at Least One Adverse Event
- Summary of TEAEs by SOC and PT
- Summary of TEAEs with an Incidence $\geq 5\%$ by SOC and PT
- Summary of Serious TEAEs by SOC and PT

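### Section 10.5 keeps unscheduled-visit readings out of every summary table, so tabulated worst values of IOP and BCVA can be understated

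*Combined protocol and SAP*

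**What the plan says.** Section 10.5 of the combined protocol and SAP sets a general rule: "Only data from nominal protocol scheduled visits will be included in the summary tables". It continues: "Data from unscheduled visits will not be included in the summary tables but will be included in the figures and listings". Several neighbouring sentences in 10.5 allow for exceptions stated elsewhere; these two do not. The same section makes minimum and maximum part of the default summary of a continuous variable.

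Section 9 provides for unscheduled examinations: "Additional exams may be scheduled as necessary to ensure the safety of the subjects during the study period". Section 2 says the same. Section 6 lists raised IOP among the corticosteroid effects, and Section 10.2 names IOP and BCVA as safety variables.

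Section 9 also sets numeric triggers:

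- IOP, as an AE: "An increase from baseline or any prior study visit of 10 mmHg in IOP in the study eye should be captured".
- IOP, as a serious AE: "An IOP of 30 mmHg or higher will be reported as an SAE".
- BCVA, as an AE: "A worsening of 3 lines or more in log of the minimum angle of resolution (logMAR) score in the study eye", measured from baseline or any earlier visit.

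Section 12.1 classes an AE as treatment-emergent by the date of first dose, whatever the type of visit. On the tables it says: "Summary tables will include the number of subjects (%) experiencing an AE and the number of AEs".

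Section 10.6 treats pre-dose data differently. All such data, "including unscheduled visits before the first dosing with study drug, will be used for the derivation of baseline value".

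**The concern.** A reading at an extra safety exam is usually taken because someone had a reason to look. For a topical steroid, IOP is the obvious reason. Such readings are more likely than routine ones to be a subject's worst, and the 10.5 rule removes them from any tabulated maximum or count above a threshold.

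The tabled maximum IOP for an arm could then be lower than a value in the same report's listings. In a dose-ranging study whose objective names safety first, a reader comparing the two strengths with vehicle would look at those tables. Listings and figures do not give a systematic comparison between arms.

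**Working it through.** The documents give no figure on this point: no mean or SD for IOP, no rate of elevation and no number of unscheduled visits. There is nothing to reproduce, so the check is of the rule's direction, its reach and an assumed range.

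**Direction.** Let S be a subject's scheduled post-dose readings and U the unscheduled ones. Then max(S) ≤ max(S and U together), with equality unless the highest reading lies in U. The same holds for the maximum rise from a fixed baseline, for the maximum BCVA loss and for the count of subjects above a threshold. The rule can only lower these quantities or leave them unchanged.

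**What the numeric triggers miss in the study eye.** Read the IOP AE rule as 10 mmHg or more, and assume whole-mmHg readings. For an eye at b mmHg at baseline with no lower earlier visit, the largest rise that meets neither IOP rule is min(9, 29 − b).

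- b = 20: min(9, 9) = 9, a reading of 29 mmHg.
- b = 22, the highest study-eye IOP the entry criteria admit: min(9, 7) = 7, again 29 mmHg.
- The condition on earlier visits matters. If any earlier visit read 19 or lower, 29 − 19 = 10 and the AE rule applies.

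For BCVA, losses under 3 lines meet no numeric rule.

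**What they miss in a treated fellow eye.** Section 2 allows the fellow eye to be dosed, but the 10 mmHg and 3-line triggers name only the study eye. As an illustration, a treated fellow eye going from 14 to 29 mmHg (+15) meets no stated numeric rule. The 30 mmHg rule names no eye, so it may cover both.

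**Scheduled coverage.** Post-dose IOP is scheduled on Days 8, 15, 28, 49 and 70.

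- From Day 1 the gaps are 8 − 1 = 7, 15 − 8 = 7, 28 − 15 = 13, 49 − 28 = 21 and 70 − 49 = 21 days.
- Dosing ends on Day 14, so readings are about weekly during exposure and the long gaps come after it.
- Subjects who do not meet the Day 15 improvement criteria go to the early discontinuation visit and have no later scheduled IOP.

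**Size under assumptions.** Take n = 40 per arm, the planned number. Let k be the subjects whose highest reading is only at an unscheduled visit, and e its excess in mmHg over their scheduled maximum. Both are assumptions. The share of subjects affected is k/40, and the arm's mean peak IOP is understated by k × e/40.

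| k | e (mmHg) | Share affected | Understatement of mean peak (mmHg) |
|---|---|---|---|
| 0 | any | 0% | 0 |
| 1 | 3 | 2.5% | 0.075 |
| 1 | 9 | 2.5% | 0.225 |
| 2 | 9 | 5% | 0.45 |
| 4 | 9 | 10% | 0.9 |

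The chance of at least one affected subject in an arm is 1 − (1 − p)^40. For an assumed per-subject probability p of 1%, 2.5%, 5% or 10%, it is 33.1%, 63.7%, 87.1% or 98.5%.

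**The case against.** The strongest reply is that little is lost. Unscheduled values stay in figures and listings. The Section 9 triggers are mandatory, but they are not a floor: the general AE rule covers anything untoward found at a study procedure, so 29 mmHg at an extra exam can be recorded as an AE on judgement. Once recorded, it enters the treatment-emergent tables whatever the visit type. This stands, and it limits the gap to readings that meet no trigger and are not judged to be AEs.

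A reader might infer more than the documents support:

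- **That by-visit means are biased.** Extra exams add to scheduled readings and do not replace them. Leaving for-cause values out of a by-visit mean need not bias it, and putting them in could.
- **That the steroid's peak IOP effect is understated as a matter of fact.** This requires a subject's highest reading to fall at an unscheduled visit, and the documents do not show that any will.
- **That the 13- and 21-day gaps leave exposure unobserved.** They fall after dosing.
- **That using unscheduled readings for baseline but not afterwards favours one arm.** The handling does differ, but it applies alike to all randomised arms, and no direction of bias follows.

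A further objection is that the available text ends within Section 12.1, so a later section on IOP or BCVA may provide worst-value summaries. That cannot be ruled out. Such a section would still conflict with the unqualified sentence in 10.5, so clarifying that sentence is worthwhile either way.

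Finally, a maximum tends to rise with the number of readings, so subjects examined more often can look worse by chance. This is a fair caution about the remedy.

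**Conclusion.** The point holds in a limited form. As written, 10.5 removes unscheduled readings from every summary table, and the available text makes no exception for safety. Tabulated worst values of IOP and BCVA can therefore be too favourable and cannot be too unfavourable. The exposed readings are study-eye IOP rises under 10 mmHg (and below 30 mmHg absolute) and BCVA losses under 3 lines, where not judged to be AEs, together with changes in treated fellow eyes.

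The size is unknown and may be zero. One affected subject is 1/40 = 2.5 percentage points of an arm. The assumed scenarios put the understatement of mean peak IOP between 0 and 0.9 mmHg. These figures rest on 40 subjects per arm, zero to four affected subjects and an excess of up to 9 mmHg, none of which is an estimate from the documents beyond the arm size. The planned efficacy analyses are not at issue. This is a cheap improvement to a descriptive Phase 2 safety report.

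**What to change.** Keep the by-visit tables on scheduled visits. Add to Section 10.5 wording such as:

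*Worst post-baseline summaries use all post-dose readings, including those from unscheduled and early discontinuation visits, and are given separately for study eyes and treated fellow eyes. For IOP they show the maximum value, the maximum increase from baseline, and the number of subjects with an increase of 10 mmHg or more and with a value of 30 mmHg or more. For BCVA they show the maximum loss and the number of subjects losing 3 lines or more. The number of readings per subject is reported by arm.*

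These cut-offs are the ones already in Section 9; no others are needed. The reading count lets the reader judge whether a higher maximum in one arm reflects more frequent examination.

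Two reconciliations go with this. If a later section already specifies worst-value summaries, align it with 10.5. Section 10.5 also labels Visits 6 and 7 as Days 84 and 98, whereas Section 2 gives Days 49 and 70. The two must agree, because those labels govern where early discontinuation readings are tabulated.

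The cost is a short addition and two extra tables from data already collected. The IOP figure may be less favourable, and the maximum depends partly on how often subjects were examined. No visit, endpoint or sample size changes.
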